2.3.2 Demographics and other baseline characteristics

For the subjects resistant or intolerant to 2 or more prior TKI treatments without MMR at inclusion to the trial, the FAS will be used for all demographics and baseline summaries and listings (except disease characteristics). For the additional subjects who were intolerant to the last TKI and were in MMR at baseline, the FAS 2 will be used for demographics and baseline summaries and listings (except disease characteristics). All the demographics and baseline characteristics will be summarized and listed for FAS and FAS 2.

Basic demographic and background data

All demographic and baseline disease characteristics data will be summarized and listed. Categorical data (e.g. age groups: 18 - <65, 65 - <75, and ≥ 75 years and 18 - <65, ≥ 65 years, sex, race, ethnicity, ECOG performance status) will be summarized by frequency counts and percentages; the number and percentage of subjects with missing data will be provided. Continuous data (e.g. age, weight, height, body mass index) will be summarized by descriptive statistics (N, mean, median, standard deviation, minimum and maximum), where BMI (kg/m^2) will be calculated as $\text{weight}[\text{kg}] / (\text{height}[\text{m}]^2)$ using weight at screening.

Diagnosis and extent of cancer

All diagnosis and extent of cancer data will be summarized. The summary table will include time (years) since initial diagnosis (descriptive statistics with N, mean, median, standard deviation, minimum and maximum) and historical mutation: present (unknown, mutant, non-mutant), historical CML-associated mutation status (E225K, E255V, E355G, T315I, etc.) (frequency counts and percentages). This table will also include extramedullary involvement: any extramedullary involvement (Yes/No) and location of extramedullary involvement (Spleen, Liver) (frequency counts and percentages).

Medical history

Medical history and ongoing conditions, including cancer-related conditions and symptoms entered on eCRF will be summarized and listed. The summary will be presented by primary system organ class (SOC) and preferred term (PT). Medical history and current medical conditions will be coded using the Medical Dictionary for Regulatory Activities (MedDRA) terminology. The MedDRA version used for reporting will be specified in the CSR and as a footnote in the applicable tables/listings.

In addition, separate listings will be produced for medical history possibly contributing to liver dysfunction, and medical history of protocol solicited cardiovascular events.

The cardiovascular risk factors, smoking, low physical activity, unhealthy diet, and others, are collected at screening and the EoT visit. A listing will be presented.

Family medical history of each subject for ischemic heart disease, cardiac arrhythmia, sudden death, high cholesterol, diabetes mellitus, heart defects (congenital heart disease), and heart failure is also collected at screening. A listing will be presented.

Other

Data collected at baseline, including informed consent for additional research on study data and biological samples, will be listed.

2.4 Treatments (study treatment, rescue medication, concomitant therapies, compliance)

2.4.1 Study treatment / compliance

The Safety set (SAF, SAF 2) will be used for the analyses below unless otherwise specified.

Duration of exposure, actual cumulative dose, average daily dose, dose intensity (DI) and relative dose intensity (RDI) will be summarized. Duration of exposure will be categorized into time intervals; frequency counts and percentages will be presented for the number (%) of subjects in each interval. The number (%) of subjects who have dose reductions or interruptions, and the reasons, will be summarized.

Subject level listings of all doses administered on treatment along with dose change reasons will be produced.

To summarize exposure data for treatment, this will be based on subjects in the corresponding Safety set with the date of last administration of study treatment and the date of first administration of study treatment.

Duration of exposure to study treatment

Duration of exposure to study treatment is considered by taking into account the duration of exposure to the investigational drug:

Duration of exposure to study treatment (weeks) = ((date of last administration of study treatment) – (date of first administration of study treatment) + 1) / 7.

The **duration of exposure in subject-years** is the total of the duration of exposure in years from all the subjects in the treatment.

The date of last administration of study treatment is defined in [Section 2.1.1](#).

Summary of duration of exposure to study treatment will include categorical summaries based on intervals (less than 24 weeks, at least 24 weeks, at least 48 weeks, at least 96 weeks) and continuous summaries (i.e. mean, standard deviation etc.).

Cumulative dose

Cumulative dose of a study treatment is defined as the total dose given during the study treatment exposure.

The **planned cumulative dose** for a study treatment refers to the total planned dose as per the protocol up to the last date of study treatment administration. The calculation for the study treatments is:

- ABL001: 80 mg/day × duration of exposure prior to dose escalation (day) + 200 mg/day × duration of exposure since dose escalation (day) (if applicable), where the starting day of dose escalation is identified as the first record in the Subject status_Dose escalation eCRF page and Study Treatment eCRF with dose increased to 200 mg once daily and reason “Lack of efficacy” at or after 48 weeks on treatment.

The **actual cumulative** dose refers to the total actual dose administered, over the duration for which the subject is on the study treatment as documented in the Study Treatment eCRF. It is the sum of the non-zero total daily doses recorded over the dosing period. For subjects who did not take any drug the actual cumulative dose is by definition equal to zero. The actual cumulative dose will be summarized.

Dose intensity and relative dose intensity

Average Daily Dose (ADD) is defined as:

ADD (mg/day) = Actual cumulative dose (mg) / Time on treatment (day).

Time on treatment (weeks) = ((date of last administration of study treatment) – (date of first administration of study treatment) + 1 – number of days with dose interruption*) / 7

*This includes the half days before and after the period with 0 dose if the treatment was interrupted after the morning dose and/or resumed in the evening (1 day record with QD dose administered before or after a record with 0 dose).

Dose intensity (DI) for subjects with non-zero duration of exposure is defined as follows:

$DI \text{ (mg/day)} = \text{Actual cumulative dose (mg)} / \text{Duration of exposure to study treatment (day)}$.

For subjects who did not take any drug the DI is by definition equal to zero.

Planned dose intensity (PDI) is defined as:

$PDI \text{ (mg/day)} = \text{Planned cumulative dose (mg)} / \text{Duration of exposure (day)}$.

Relative dose intensity (RDI) is defined as follows:

$RDI = DI \text{ (mg/day)} / PDI \text{ (mg/day)}$.

ADD, DI and RDI will be summarized separately for the two dose regimens.

Dose changes, interruptions or permanent discontinuations

The number of subjects who have dose increase, dose reductions, dose interruptions or permanent discontinuations, and the reasons, as well as the duration of dose interruption due to any reason will be summarized. For any subject, duration of dose interruption will be calculated by adding all individual episodes of dose interruption for that subject. This includes the half days before and after the period with 0 dose if the treatment was interrupted after the morning dose and/or resumed in the evening (1 day record with QD dose administered before or after a record with 0 dose).

‘Dose Changed’, ‘Dose Interrupted’ and ‘Dose Permanently Discontinued’ fields from the Study Treatment eCRF and Disposition pages will be used to determine the dose changes, dose interruptions, and permanent discontinuations, respectively.

The corresponding fields ‘Reason for Dose Change’ and ‘Reason for Permanent Discontinuation’ will be used to summarize the reasons.

A dose change occurs when total daily dose is different from the most recently planned dose. Before week 48, there is only one planned dose, i.e. 80 mg/day. For subjects not in MMR at 48 weeks or losing the response after the week 48 assessments up to week 108, a dose escalation to 200 mg q.d. may be considered for subjects on 40 mg b.i.d. or 80 mg q.d., if in the investigator’s opinion the subject may benefit from the escalation.

For the purpose of summarizing interruptions and reasons, multiple entries for interruption that are entered on consecutive days with different reasons will be counted as separate interruptions. However, if the reason is the same in the mentioned multiple entries on consecutive days, then it will be counted as one interruption.

Reduction: A dose change where the actual total daily dose is lower than the most recently planned dose. Therefore any dose change to correct a dosing error will not be considered a dose reduction. Only dose change is collected in the eCRF, while number of reductions will be derived programmatically based on the change and the direction of the change.

Increase: A dose change where the actual total daily dose is greater than the most recently planned dose. Therefore any dose change to correct a dosing error will not be considered a dose increase. Only dose change is collected in the eCRF, while number of increase will be derived programmatically based on the change and the direction of the change.

For the subjects with dose escalation after week 48, the subjects who are on treatment, complete treatment or have permanent discontinuations will be summarized on SAF by means of descriptive statistics separately.

The additional subjects who were intolerant to the last TKI and were in MMR already at baseline will be assessed for the duration of exposure in days to asciminib, as well as the dose intensity (computed as the ratio of actual cumulative dose received and actual duration of exposure) and the relative dose intensity (computed as the ratio of dose intensity and planned dose intensity), and dose change and permanent discontinuation will be summarized by means of descriptive statistics using SAF 2.

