4.1 Rationale for study design

The trial presented in this protocol is an open-label, treatment optimization study. Patients will receive asciminib as study treatment continuously for up to 144 weeks or until disease progression, treatment failure or intolerance to treatment. At treatment initiation, asciminib will be provided to all trial patients at a total daily dose of 80 mg. All patients will be randomly assigned 1:1 to 2 groups with 80 mg given either as 40 mg b.i.d. or 80 mg q.d., using IRT to avoid any selection bias. Considering the objective nature of the primary endpoint, an open label study is deemed acceptable.

The ongoing ASCEMBL study is a phase III study, investigating the efficacy of treatment with asciminib versus bosutinib in CML-CP patients with at least 2 prior therapies. In the primary analysis, asciminib (40 mg b.i.d.) demonstrated statistically significant superiority and clinically meaningful efficacy when compared to bosutinib (500 mg q.d.) with a MMR rate at week 24 of 25.5% over 13.2% respectively. Following the release of the initial results, questions remain such as daily dosing schedule and escalation.

Changing from a twice a day (b.i.d.) to once a day (q.d.) dosage for asciminib may improve the ease of administration, increase the compliance with treatment and thus help to maintain treatment outcomes. Though the trial will not be powered to compare both treatments, the descriptive data from both treatment groups is expected to provide additional insight into optimal patient management.

Patients treated in later lines of CML often have few remaining therapeutic options. Considering asciminib has demonstrated activity and tolerability in dosages of up to 200 mg b.i.d. (Hughes et al 2019), it is of interest to investigate whether patients could benefit from a potential asciminib dose escalation. A single step dose escalation to 200 mg q.d. was chosen for this trial as it would allow for a substantial increase in asciminib exposure while at the same time the safety profile can be maintained.

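### The half-day interruption rule in SAP 2.4.1 has no regimen condition, so a full once-daily dosing day next to a gap can be counted as part-interrupted and ADD can exceed the dose taken (minor)

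*SAP*

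**What the plan says.** SAP 2.4.1 builds ADD from two quantities:

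- **Numerator:** the actual cumulative dose: "It is the sum of the non-zero total daily doses recorded over the dosing period".
- **Denominator:** time on treatment, which is last dose date minus first dose date plus 1, less the days of dose interruption.

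A footnote to the interruption days reads "This includes the half days before and after the period with 0 dose", for the case where dosing stopped once a morning dose had been taken or restarted with an evening dose. It gives the identifying pattern as a "1 day record with QD dose administered before or after a record with 0 dose". The same rule appears again in the paragraph on dose changes and interruptions, where it sets the total duration of interruption.

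DI divides the same cumulative dose by the whole duration of exposure, and RDI is DI over planned dose intensity. Neither uses interruption days. For display, "ADD, DI and RDI will be summarized separately for the two dose regimens".

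**The concern.** The footnote describes a b.i.d. situation: the morning dose was taken and the evening dose was not, or the reverse. For a b.i.d. subject, a one-day record with a once-daily frequency beside a zero-dose record does mean half a day's drug.

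In the 80 mg q.d. group every dosed record is once daily, and so is every record after escalation to 200 mg q.d., whichever group the subject was randomized to. There, a one-day record beside a gap is a full dosing day. A q.d. subject who doses in the morning and then stops also satisfies the words about interruption after the morning dose. Protocol 6.6.5 says that total daily dose, start and end dates and dosing are collected, and it names no time of day. The record pattern is therefore what a programmer would be left to use.

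What is at stake is the accuracy of two descriptive exposure outputs, interruption duration and ADD. Protocol 4.1 gives as a reason for once-daily dosing that it may "increase the compliance with treatment and thus help to maintain treatment outcomes", so exposure tables split by regimen will be read with some care. An ADD above the highest dose taken would be visibly wrong.

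**Working it through.** The documents report no ADD or interruption figure to reproduce, so the SAP formulas are applied to constructed cases. ADD is taken in mg/day with time on treatment in days. (The SAP formula for time on treatment divides by 7 and so gives weeks, while the ADD formula asks for days.)

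**Single gap.** Inputs: 336 days of exposure (48 weeks), planned 80 mg/day, and 14 day-equivalents of drug missed (assumed). Cumulative dose = 80 × (336 − 14) = 25,760 mg.

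| Case | Interruption days | Time on treatment (days) | ADD (mg/day) | DI (mg/day) |
|---|---|---|---|---|
| q.d., 14 zero days, no half days added | 14 | 322 | 25,760/322 = 80.00 | 76.67 |
| q.d., same gap with a 1-day record on each side, rule as worded | 14 + 0.5 + 0.5 = 15 | 321 | 25,760/321 = 80.25 | 76.67 |
| b.i.d., 13 zero days and two days at 40 mg, rule as worded | 13 + 0.5 + 0.5 = 14 | 322 | 80.00 | 76.67 |
| b.i.d., same, without the rule | 13 | 323 | 25,760/323 = 79.75 | 76.67 |

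The rule gives the right answer on b.i.d. and the wrong one on q.d. RDI is 76.67/80 = 0.958 in every row.

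**Random misses on q.d. over 144 weeks.** Inputs: 144 × 7 = 1008 days; each daily dose missed independently with probability q (assumed 5% or 10%); consecutive days at the same dose held as one record. A one-day dosed record is then a dosed day with a missed day on each side. Ignoring the two ends of the period:

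- Expected number of such days = 1008 × q² × (1 − q). At 5%: 1008 × 0.0025 × 0.95 = 2.39. At 10%: 1008 × 0.01 × 0.90 = 9.07.
- Each such day borders two gaps. If both half days are taken, it loses a whole day, so these counts are also the false interruption days. The true interruption days are 1008q = 50.4 and 100.8.
- ADD = 80(1 − q)/[(1 − q) − q²(1 − q)] = 80/(1 − q²). At 5%: 80/0.9975 = 80.20. At 10%: 80/0.99 = 80.81.
- If each record loses only one half day, the false days are about 1.2 and 4.5, and ADD = 80/(1 − q²/2) = 80.10 and 80.40.

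A simulation of 400 such subjects agreed: 52.8 counted against 50.4 true days at 5%, 109.7 against 100.5 at 10%, and ADD 80.20 and 80.82.

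**Dependence on record splitting.** In a 336-day course with 14 separate one-day gaps, suppose each gap has its own one-day records on both sides. The rule then counts 14 + 14 = 28 days, and ADD = 25,760/308 = 83.64. This is an extreme. With long multi-day records around each gap, the rule is never triggered and the error is zero.

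**The case against.** The best reply is that the intention is plain. The morning and evening wording describes b.i.d. dosing, a careful programmer would apply it only there, and an ordinary multi-day q.d. record does not meet the one-day condition. The outputs are also descriptive: SAP 2.1 says that the two groups are not for comparison, every dose is listed by subject, and no test uses ADD. All of this stands and keeps the point minor. It does not make the wording right, because the stated record pattern fits a fully dosed q.d. day.

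A reader might go further and infer that the exposure rules as a whole favour q.d. At 5% of doses missed at random, b.i.d. ADD is 80(1 − q)/(1 − q²) = 80/1.05 = 76.19, against 80.20 on q.d., a gap of about 4.0 mg/day. The documents do not support that reading:

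- The half-day rule supplies only 80.20 − 80.00 = 0.20 of the gap. The rest follows from the ordinary definition of ADD as dose per day on treatment. A zero-dose day leaves the denominator, while a 40 mg day stays in and fits the SAP's definition of a reduction: "A dose change where the actual total daily dose is lower than the most recently planned dose".
- The gap needs b.i.d. misses to be mostly isolated single doses. If whole days are missed, ADD is the same in both regimens.
- Interruption duration points the other way. In the 336-day example, 28 isolated missed b.i.d. doses give 0 interruption days, against 14 on q.d. for the same missed drug.
- DI and RDI, in the same by-regimen summary, are equal for equal missed drug.

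**Conclusion.** The rule is wrong as written, and the consequence is minor. The half-day rule is correct for a b.i.d. subject who took one of two doses and incorrect for any once-daily record. It overstates interruption duration on q.d. and can raise ADD above the dose taken.

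Under independent random misses over 1008 days, with consecutive equal doses kept as one record, the excess is about 2.4 days per q.d. subject at 5% missed and about 9 at 10%, or half that if each record loses only one half day. ADD is then about 80.2 and 80.8 instead of 80.0 mg/day. The miss rates and the record structure are assumptions.

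DI, RDI, the primary endpoint, alpha, power and sample size do not change. The point does not extend to a claim that the planned summaries generally flatter q.d., nor to a case for removing ADD.

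**What to change.** In both paragraphs of SAP 2.4.1 that carry the rule (the footnote to time on treatment, and the paragraph on duration of dose interruption), apply the half-day adjustment only to records of a subject who is on a b.i.d. regimen at that date and took one of the two daily doses. The condition should follow the regimen at the date, not the randomized group, so that records at 200 mg q.d. are also excluded.

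Keep ADD. Add a footnote to the by-regimen table saying that ADD leaves out whole zero-dose days but includes days with one missed b.i.d. dose, so DI and RDI are the measures to read for drug taken by regimen.

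The cost is one clause in two places, one condition in the exposure program and one table footnote. No new data are needed.

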2.4.2 Prior, concomitant and post therapies

Prior anti-cancer therapy

The number and percentage of subjects who received any prior anti-neoplastic medications will be summarized for the lowest anatomical therapeutic classification (ATC) class and preferred term. A listing will also be produced.

Anti-neoplastic medications will be coded using the WHO Drug Dictionary (WHO-DD). Details regarding WHO-DD version will be included in the footnote in the tables/listings.

The above analyses will be performed using the FAS and FAS 2.

The following information will also be summarized for the FAS and FAS 2:

- Prior TKI by medication (e.g. imatinib, dasatinib, nilotinib, ponatinib, bosutinib, etc.)
- Number of prior TKI (e.g. 2, 3, 4, etc.)
- Number of lines of prior TKI therapy (2, 3, 4, 5+)
A new line of therapy is considered each time a change in TKI occurred. Multiple entries for the same TKI will be counted as separate lines of therapy if a different TKI is received between the different entries.
- Time on each line of prior TKI therapy (in years)
- Time on last prior TKI (in years)
- Reason to discontinue the most recent TKI therapy at the time of screening
- Prior non-TKI therapies (Yes, No).

A Sankey-like plot showing the sequence of prior TKIs will be provided.

Post treatment anti-cancer therapy

Anti-neoplastic therapies since discontinuation of study treatment will be listed and summarized by the lowest anatomical therapeutic classification (ATC) class and preferred term by means of frequency counts and percentages using FAS and FAS 2.

Anti-neoplastic medications will be coded using the WHO-DD. Details regarding WHO-DD version will be included in the footnote in the tables/listings.

Concomitant therapies

Concomitant therapies are defined as all interventions (therapeutic treatments and procedures) other than the study treatment administered to a subject coinciding with the study treatment period. Concomitant therapies include medications (other than study drugs) and medical procedures starting on or after the start date of study treatment, or starting prior to the start date of study treatment and continuing after the start date of study treatment.

Concomitant medications will be coded using the World Health Organization (WHO) Drug Reference Listing (DRL) dictionary that employs the WHO ATC classification system and summarized by the lowest ATC class and PT using frequency counts and percentages. Surgical and medical procedures will be coded using MedDRA and summarized by SOC and PT.

The summaries for the on-treatment period using the Safety Set (SAF, SAF 2) will include:

- Therapies starting on or after the start of study treatment but no later than the end of the on-treatment period and
- Therapies starting prior to start of randomized study treatment and continuing after the start of study treatment.

All concomitant therapies will be listed using the Safety Set (SAF, SAF 2). Any concomitant therapies starting and ending prior to the start of study treatment or starting beyond end of the on-treatment period will be flagged in the listing.

The prohibited concomitant medications will be summarized by lowest ATC class and preferred term up to the end of on-treatment period. Prohibited medications will be concomitant medications that led to the protocol deviation “Use of prohibited concomitant medication”.

2.5 Analysis supporting primary objective(s)

In this section, the targeted treatment effect corresponding to the primary objective as well as the primary objective is clarified using the estimand language.

The primary clinical question of interest is: What is the effect of asciminib in CML subjects in chronic phase who were resistant or intolerant to 2 or more prior TKIs, with regards to achieving MMR at 48 weeks while on study treatment regardless of dose modification, dose interruption, or any intake of concomitant medications and without intake of prohibited medications.

The primary estimand is described by the following attributes:

1. The target population comprises CML Subjects with resistance or intolerance to 2 or more prior TKI per the 2020 ELN recommendations.
2. Endpoint: Major Molecular Response (MMR) achieved at week 48 while on study treatment without meeting any treatment failure criteria prior to week 48. A subject will be counted as having achieved MMR at week 48 if he/she meets the MMR criterion ($BCR::ABL1 \leq 0.1\% IS$) at week 48 while on study treatment unless the subject met any treatment failure criteria prior to week 48.

3. Treatment of interest: the investigational treatment asciminib received for at least 48 weeks, with or without dose modification, dose interruption or any intake of concomitant medications, or intake of prohibited medications.
4. The intercurrent events are the events occurring after first dose of study drug that may impact the treatment effect. The intercurrent events of interest are:
 - a) Treatment discontinuation (i.e. having performed an EOT visit) prior to week 48 due to any reason
 - b) Dose modification or dose interruption, or any intake of concomitant medications
 - c) Intake of prohibited medications
5. The summary measure is the MMR rate and its 95% confidence interval at week 48.

The primary analysis will be conducted after all randomized subjects have been on study treatment for 48 weeks or discontinued earlier, i.e., LPFT + 48 weeks.

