6.2.2 Prohibited medication

Other anticancer agents

The administration of any other anticancer agents including chemotherapy and biologic agents is not permitted except for anti-cancer treatments of newly diagnosed solid cancers (e.g. prostate cancer) that would not impact the level of minimal residual disease of patients. These patients may remain in the current study after consultation with Novartis. The administration of other tyrosine kinase inhibitors indicated for treatment of CML is not allowed.

Rescue medication

Not applicable.

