- **For the intercurrent events 4c:** The hypothetical strategy will be applied for the intake of any prohibited medication. The interest focuses on the treatment effect if patients had not taken prohibited medications prior to week 48.

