2.5.3 Handling of intercurrent events

The approach of accounting for intercurrent events is as follows:

- **For the intercurrent events 4a:** The composite strategy will be applied for treatment discontinuation due to any reason. Treatment discontinuations due to any reason will be defined as non-responders.
- **For the intercurrent events 4b:** The treatment policy strategy will be applied. Meaning, the actual values of the variable (BCR::ABL1 % IS) will be used, regardless of whether the intercurrent event has occurred.
- **For the intercurrent events 4c:** The treatment policy strategy will be applied. Meaning, the actual values of the variable (BCR::ABL1 % IS) will be used, regardless of whether the intercurrent event has occurred.

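### The SAP's primary question excludes prohibited medication but its 4c rule ignores it, so a Week 48 MMR in the few patients taking another anticancer agent or CML TKI alongside asciminib would count as a response

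*SAP*

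**What the plan says.** Four places in the two documents define how prohibited medication enters the primary estimand.

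- **SAP 2.5, clinical question.** MMR at 48 weeks is sought on study treatment, regardless of dose modification, interruption or "any intake of concomitant medications and without intake of prohibited medications".
- **SAP 2.5, attribute 3 (treatment of interest).** Asciminib is received for at least 48 weeks "with or without dose modification, dose interruption or any intake of concomitant medications, or intake of prohibited medications". SAP 1.2.1 has the same attribute, and its version of the clinical question contains no exclusion.
- **SAP 2.5.3, event 4c (intake of prohibited medications).** Treatment policy applies: "the actual values of the variable (BCR::ABL1 % IS) will be used, regardless of whether the intercurrent event has occurred".
- **Protocol 12.4.3, event 4c.** "The hypothetical strategy will be applied for the intake of any prohibited medication", with the explanation that "The interest focuses on the treatment effect if patients had not taken prohibited medications prior to week 48".

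Protocol 6.2.2 defines what is prohibited: other anticancer agents, including chemotherapy and biologics, apart from certain treatments for new solid cancers that would not affect residual disease. On CML drugs it is explicit: "The administration of other tyrosine kinase inhibitors indicated for treatment of CML is not allowed".

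The SAP's list of changes says that the strategies for 4a and 4c were updated. SAP section 4, which is the place for changes to protocol-specified analyses, says that none apply.

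**The concern.** The question excludes an event that the analysis rule then disregards. A reader of the result cannot tell whether the reported rate describes asciminib alone or asciminib with whatever else was taken.

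The direction of any effect is also clear. The endpoint is the BCR::ABL1 level, and other CML TKIs are given to lower it. The trial tests one pooled group against a fixed 23%, so no comparator arm has the same event. For a patient in MMR at Week 48 while also taking another CML drug, the 4c rule can only add to the count of responders. Neither sensitivity analysis in SAP 2.5.5 addresses this: one removes the imputation of a missing Week 48 PCR, and the other excludes patients whose data are missing because of COVID-19.

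**Working it through.** **Step 1. Which patients does rule 4c decide?** Each other rule removes some of those who take a prohibited drug before Week 48.

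| Situation before Week 48 | Rule | Week 48 status |
|---|---|---|
| Stops asciminib, EOT visit performed | SAP 2.5.3, 4a (composite, any reason) | Non-responder |
| Meets a treatment failure criterion (SAP 5.4.4: e.g. confirmed loss of MMR, loss of CHR, progression to AP/BC) | SAP 2.5, attribute 2 | Non-responder |
| PCR taken after the EOT visit or after failure | SAP 2.1.1 (excluded from efficacy analyses) | Not used |
| Takes the drug with asciminib, no EOT visit, no failure, in MMR at Week 48 | SAP 2.5.3, 4c (treatment policy) | **Responder** |

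Protocol 9.1.1 requires study treatment to stop when prohibited treatment is used, so the last row should be rare. It is not empty by construction. Event 4a is identified by an EOT visit before Week 48, so a late or missed discontinuation does not trigger it.

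**Step 2. Reproduce the design.** Inputs from SAP 2.5.2 and section 3: n = 156, null rate 0.23, alternative 0.33, one-sided exact test at 0.025, stated power 80%.

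With X ~ Binomial(n, p), P(X ≥ r) is the sum of C(n, x) p^x (1 − p)^(n − x) for x = r to n. The Clopper-Pearson lower limit is the 2.5th percentile of Beta(r, n − r + 1).

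| r | r/156 | P(X ≥ r) at 0.23 | P(X ≥ r) at 0.33 | Lower 95% limit |
|---|---|---|---|---|
| 46 | 29.5% | 0.0363 | 0.846 | 22.47% |
| 47 | 30.1% | 0.0241 | 0.801 | 23.05% |

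The critical count is 47, and the stated 80% power reproduces (0.801). The source of the null also reproduces: 6/54 = 11.1%, with 95% limits 4.2% and 22.6%.

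**Step 3. Size per patient.** 1/156 = 0.64 percentage points.

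**Step 4. Illustration.** The documents give no frequency of prohibited use, so the number affected is an assumption, shown over a range. Suppose k patients who would otherwise be non-responders count as responders under 4c, and the other 156 − k respond at 23%. The chance of rejecting is P(X ≥ 47 − k) with X ~ Binomial(156 − k, 0.23).

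| k | Added to observed rate (points) | Chance of rejecting |
|---|---|---|
| 0 | 0 | 2.4% |
| 1 | 0.64 | 3.3% |
| 2 | 1.28 | 4.4% |
| 3 | 1.92 | 5.8% |
| 5 | 3.21 | 9.7% |

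This is an upper reading for each k, because it takes every affected patient to be a non-responder on asciminib alone.

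**The case against.** The strongest case is that this is leftover wording. SAP 1.2.1, attribute 3 in both places and the 4c rule agree with one another, the analysis invokes the ITT principle, and the change list shows that the strategy was updated on purpose. On that view only one clause in SAP 2.5 is out of line, and deleting it restores consistency. Choosing treatment policy for a rare protocol violation is a legitimate judgement. The composite strategy is not the protocol's choice either, since the protocol used a hypothetical one.

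Much of this stands. Deleting the clause would make the SAP coherent, and that is the minimum acceptable repair. It would not record the departure from Protocol 12.4.3. It would also leave a rule that can only favour the drug in a single-group test, with nothing to show by how much. Attribute 3 is weak evidence of deliberate alignment, because the protocol has the same attribute beside its hypothetical strategy.

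Two further points are fair. Any exact test has a boundary that one patient can cross, and at the design rate of 33% about 51 responders are expected (0.33 × 156 = 51.5) against a critical count of 47. Cases would also be visible: SAP 2.4.2 tabulates prohibited medications and SAP 2.3.1 lists all protocol deviations. But a listing does not say how the primary count would be reclassified.

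A reader might infer that any MMR reached on another TKI would be credited to asciminib. The documents do not support that: a patient who switches and has an EOT visit before Week 48 is a non-responder under 4a. Nor do they say that every prohibited agent acts on BCR::ABL1; the list covers anticancer agents generally.

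**Conclusion.** The contradiction is real and unresolved. The clinical question in SAP 2.5 conflicts with attribute 3, with SAP 1.2.1 and with the 4c rule, and SAP section 4 does not record the change from the protocol's hypothetical strategy.

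The effect on the result is confined to patients taking another anticancer agent or CML TKI together with asciminib, with no EOT visit before Week 48 and no earlier failure, who are in MMR at Week 48. Each one adds 0.64 points. Given the discontinuation rule few are expected, but that is a judgement, since no frequency is stated.

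It would go too far to conclude that the primary test is invalid or that its error rate is inflated in practice. The rejection chances above hold only if such patients occur and would not have responded on asciminib alone. The sample size and power are unaffected. The point is worth correcting because the estimand should be stated one way and the remaining ambiguity can be bounded at almost no cost.

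**What to change.** 1. In SAP 2.5, 1.2.1 and 2.5.3, make the clinical question, attribute 3 and the 4c strategy say the same thing.
2. In SAP section 4, record that the handling of 4c departs from the hypothetical strategy in Protocol 12.4.3, with the reason.
3. Preferred: in the primary analysis, count as a non-responder any patient who took, before Week 48, another anticancer agent or CML TKI prohibited by Protocol 6.2.2. This matches the treatment of 4a. Report the treatment-policy result as a sensitivity analysis.
4. If the sponsor keeps treatment policy as primary, remove the exclusion from the question in SAP 2.5 and add the non-responder version to SAP 2.5.5 as a bound.

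The cost is SAP wording and one extra run of the same exact test. Under option 3 the MMR count may fall slightly, and a patient with only brief exposure to a prohibited agent would also be counted as a non-responder, which errs on the conservative side. The change concerns classification in the analysis only, not patient management.
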